5. STUDY POPULATION

5.1. Population description

Thirty-five participants of both genders, aged between 21 and 65 years, with laboratory (genetic) diagnosis of Huntington's disease and presenting the eligibility criteria determined for the study will be included.

5.2. Inclusion and exclusion criteria

The inclusion and exclusion criteria of the study are:

5.2.1. Inclusion criteria

- a) Providing informed consent in writing, signed and dated;
- b) Participant of both genders aged ≥ 21 and ≤ 65 years*;
- c) Present confirmatory diagnostic report (PCR) of Huntington's disease with a number of CAG repeats on chromosome 4, greater than or equal to 40 and less than or equal to 50 (if the participant has not taken the exam and/or if he does not have the exam report accessible, a new examination should be performed);
- d) Getting 5 points or more in the motor evaluation of the UHDRS scale (*Unified Huntington's Disease Rating Scale*) at the time of inclusion;
- e) Obtaining 8 to 11 points in the functional capacity of the UHDRS scale at the time of inclusion.

*Note: The age of the participant will be considered on the day of the inclusion visit (V-3).

5.2.2. Exclusion criterion

- a) Participant of the research who has participated in protocols of clinical studies in the last 12 (twelve) months, unless the researcher considers that there may be direct benefit to it (Resolution CNS 251, of August 7, 1997, item III, subitem J);
- b) Diagnosis of juvenile Huntington's disease*;
- c) Diagnosis of epilepsy;
- d) Diagnosis of major cognitive disorder;
- e) Decompensated active psychiatric disease;
- f) Current or past history of neoplasia;

- g) Current history of severe and uncontrolled gastrointestinal, hepatic, renal, endocrine, pulmonary, hematological, immunological, metabolic, or cardiovascular disease;
- h) Diagnosis of any active infection, be it viral, bacterial, fungal or caused by another pathogen;
- i) Participant who has contraindication to the tests performed in this study, such as having a pacemaker or surgical clip;
- j) Alcohol and drug abuse (previous diagnosis according to the criteria of the Diagnostic and Statistical Manual of Mental Disorders - DSM V);
- k) Use of illicit drugs;
- I) Present positive results in one of the serological tests: HIV 1 and 2 (Anti-HIV-1.2), HTLV I and II, HBV (HBsAg, Anti-HBc), HCV (anti-HCV-Ab) and FTA-ABS (Treponema pallidum);
- m) History of drug allergy, including contrasts for imaging, or bovine products;
- n) In use or foresight of the use of immunosuppressive drugs or prohibited drugs (item 6.9) during the first three months after the first administration of the investigational product;
- o) Any clinical change that is interpreted by the Investigator physician as a risk to the inclusion of the participant in the study.

*Note: The diagnosis of juvenile Huntington's will be defined by the presence of 60 or more CAG repeats in the confirmatory diagnostic report for the disease and the appearance of characteristic signs and symptoms before the age of 21 (Nance, 2001).

5.2.3. Discontinuation criteria (interruption) of treatment with the investigational product:

Study participants are free to withdraw their consent and/or discontinue their participation in the study at any time, without prejudice to further treatment, as well as penalty or loss of benefits.

In addition to withdrawing consent, study participants may be discontinued for any of the reasons described below:

- a) Study abandonment or loss of follow-upa;
- b) Adverse events at the investigator's discretion^b;

- c) Fulfilling any of the exclusion criteria of the study (newly developed or not previously identified criteria), which at the investigator's discretion prevents him from remaining in the study (risk x benefit assessment);
- d) Violation of the protocol, at the discretion of the Investigator and/or Sponsor;
- e) Discontinuation of the study by Sponsor;
- f) Death;
- g) Need for the use of prohibited concomitant medications that at the investigator's discretion may interfere with the results of the investigational product of the study (item 6.9);
- h) Any other clinical, laboratory or psychological condition, which in the opinion of the Investigator, is likely to discontinue treatment.

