1.3. Therapeutic target: Huntington's disease (HD)

Huntington's disease (HD) is a fatal, genetic, highly debilitating and progressive neurodegenerative disorder characterized by the following clinical signs and symptoms: cognitive, motor and psychiatric dysfunction. Usually, the onset of symptoms of the disease occurs between 25 and 45 years of age (ranging from 3-70 years). Once started, cognitive-behavioral symptoms and engines progress inexorably until they result in a fatal outcome. The most striking sign of the disease is the presence of involuntary movements, called choreic movements, which are continuous, brief, random and result in contractions of the orofacial muscle and limbs (Ross et al., 2014; Nuzzo et al., 2014). Emotional changes and behavioral changes

Clinical Protocol: ADORE-DH Sponsor: Cellavita Pesquisa Científica LTDA Amendment 6 dated February 23, 2021.

that result in anxiety and depression, although frequent, do not occur uniformly among patients, as motor and cognitive alterations occur (Ross et al., 2014).

Several factors alter the overall prevalence of the disease, such as: different ethnicities, geography, migration patterns and location. The disease has a global prevalence of about 5.7 cases per 100,000 people in the Western world, and the incidence is more prevalent in descendants of Western Europe, North and South America and Australia, and rare in Africans and Asians (Olanow and Schapira, 2012; Gonçalves, 2013). HD is an autosomal dominant genetic disorder caused by a mutation in the huntingtin protein gene (HTT), located on the short arm of chromosome 4 (location 4p 16.3). This genetic mutation causes increased repetition of the CAG trinucleotide sequence (responsible for encoding the glutamine). This abnormal repetition expanded produces a protein with a long chain of glutamine, known as polyglutamine or PolyQ, in the N-terminal region of exon 1 of the gene, which constitutes the abnormal huntingtin protein (Figure 1) (Squitieri et al., 2006; Gonçalves, 2013; Ross et al., 2014; Nuzzo et al., 2014). HD is one of the 9 PoliQ disorders, which additionally include spinocerebellar ataxias (ACE type 1, 2, 3, 6, 7 and 17), bulbospinal muscular atrophy and dentorubro-palidoluisian atrophy (DRPLA), and among these, HD is the most prevalent (Schols et al., 2004).

[figure not shown]

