1.3.1. Pharmacological approach

The medications most commonly prescribed for these patients include antipsychotics, anxiolytics, antidepressants, mood stabilizers and, in patients with juvenile HD, anticonvulsants. Dopamine-blocking agents, such as tetrabenazine, which has been approved by the United States of America (USA), can control the symptoms of chorea (Hayden et al., 2009; Wang et al., 2010). The same antipsychotic medications such as haloperidol, clozapine, chlorpromazine and olanzapine are prescribed to reduce chorea as they have dopamine antagonistic action and, additionally, the benefit of controlling the behavioral and/or psychotic characteristics that HD patients may present (Jankovic, 2009; Phillips et al., 2008).

To deal with symptoms of depression, suicidal thoughts and impulsiveness, Antidepressant medications (fluoxetine, escitalopram, sertraline, paroxetine and venlafaxine) are often prescribed for HD patients. In addition, anxiolytic medicines such as diazepam, benzodiazepines (Clonazepam, Alprazolam), paroxetine and venlafaxine are indicated to calm patients and mitigate anxiety symptoms associated with the disease (Phillips et al., 2008; Kaplan and Stockwell, 2012).

For mood stabilization, drugs such as lithium, valproate and carbamazepine can be prescribed to patients (Bonelli and Wenning, 2006). There are a lot of medications that can be used to control HD, however, many of these cause adverse effects that can worsen the patient's functionality and quality of life. To date, there is no adequate treatment for the inevitable cognitive and motor decline observed in HD progression (Olanow & Schapira, 2012).

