#### 7.2. Data Handling

#### 7.2.1. Premature Withdrawal and Missing Data

The following imputation rules will be used for prior and concomitant medications.

Partial or missing start date for concomitant medication

- 1. Incomplete or partial start date will not be imputed if end date of concomitant medication is on or before treatment start date.
- 2. Incomplete or missing start date will be imputed as mentioned below if end date of concomitant medication falls after treatment start date (or if medication is ongoing at EoS for treated participants).

Handling of partial/missing dates for Medication

Partial/Missing Start Date

- 1. Missing day Impute the 1st of the month unless month and year is same as month and year of first dose of study drug then impute first dose date.
- 2. Missing day and month impute 1st January unless year is the same as first dose date then impute first dose date.

Partial/Missing End Date

- 1. Missing day Impute the last day of the month unless month and year is same as month and year of last dose of study drug then impute last dose date.
- 2. Missing day and month impute 31st December unless year is the same as last dose date then impute last dose date.

No other imputation of missing data for safety assessments will be made. Wherever possible missing data will be summarized as a category.

No imputation for missing data will be made as the mixed model repeated measures incorporates missing data.

Additional analyses may be conducted for FDA, EMA or other regulatory agencies if required and deemed appropriate under assumptions of MAR and MNAR using MI.

The eCRF did not allow entry of partial AE dates so no imputation of start or stop dates will be performed.

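### Protocol 5.2.3(c) does not separate stopping infusions from leaving the study, so outcome data can be lost for reasons related to Huntington severity

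*Protocol*

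**What the plan says.** **Who may be discontinued.** Protocol 5.2.3 opens permissively: "study participants may be discontinued for any of the reasons described below". Item c then reads "Fulfilling any of the exclusion criteria of the study (newly developed or not previously identified criteria" and continues "which at the investigator's discretion prevents him from remaining in the study (risk x benefit assessment". The visit schedule has discontinuation criteria checked at every visit from V1 to V11.

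**Which criteria carry over.** Protocol 5.2.2 includes item d, "Diagnosis of major cognitive disorder", and item e, "Decompensated active psychiatric disease". Item c exempts neither when the cause is Huntington's disease.

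**How the protocol describes the disease.** Section 1.3 calls it "characterized by the following clinical signs and symptoms: cognitive, motor and psychiatric dysfunction", and 1.3.1 says that "there is no adequate treatment for the inevitable cognitive and motor decline observed in HD progression".

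**What happens afterwards.** Protocol 5.5 provides no further follow-up for participants excluded over a study criterion once adverse events are ruled out. Protocol 5.4 allows no replacement after randomisation. Protocol 7.5, by contrast, keeps participants who miss an administration in the study.

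**How the data are analysed.** The SAP primary endpoint is the annual TMS slope (4.1.1). The model has treatment, baseline TMS and treatment by day, fitted to observed data (7.4.1). On missing data SAP 7.2.1 says "No imputation for missing data will be made as the mixed model repeated measures incorporates missing data". Multiple-imputation analyses under MAR or MNAR are optional, for use if regulators ask.

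**The concern.** Cognition and behaviour are domains of the protocol's primary variable (3.1.1) and secondary endpoints in the SAP (4.1.2). Newly meeting item d or e is therefore likely to coincide with worsening on scores that the trial measures. If the participant then leaves the study, the rest of that course is not observed, and the reason is tied to severity.

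If the product slows the disease, more placebo than active participants would be expected to reach such a threshold, so the placebo decline would be cut short more often. The planned model treats the missing values as explained by the TMS values already seen. It has no cognitive or behavioural term, and no MNAR analysis is firmly planned. With 7 placebo participants, each early exit weighs heavily.

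**Working it through.** **1. Does the route exist in the text?** Set side by side:
- The 5.2.3 heading concerns interrupting the product; item c concerns staying in the study. The two are not distinguished.
- Item c covers any newly met exclusion criterion, so d and e are included.
- 5.5 stops follow-up for criteria-based exclusions. Stopping infusions under item c can thus end UHDRS collection.
- 7.5 shows that the protocol already accepts study participation without every infusion.

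The route exists, but it is discretionary.

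**2. Weight of one participant.** Allocation is 35 x 2/5, 2/5, 1/5 = 14, 14, 7, as stated. One withdrawal is 1/7 = 14.3% of placebo, against 1/28 = 3.6% of pooled active.

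**3. Possible size for the TMS slope.** The documents give no SD, effect size, dropout rate or number of item c withdrawals. These inputs are assumed:
- Placebo slope 4 points/year, slope SD 4, visit SD 3; 28 v 7 participants; 12 visits 30 days apart; 4,000 runs per setting.
- A latent cognitive/psychiatric course has correlation r = 0.3, 0.6 or 0.9 with the TMS slope.
- A participant is withdrawn when that course passes a cut-off met by q = 15% or 30% of placebo (7 x 0.15 = 1.05 or 7 x 0.30 = 2.1 people). Faster courses tend to leave earlier.
- Estimator: each participant's least-squares slope, weighted by 1/(4² + 3²/Sxx), where Sxx is the sum of squared deviations of that person's visit times. This stands in for the planned mixed model.

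True difference -3 (placebo 4, active 1):

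| r | q | withdrawn, placebo / active | all visits | after withdrawal | shrinkage from -3 |
|---|---|---|---|---|---|
| 0.3 | 15% | 14.8% / 10.4% | -2.95 | -2.92 | 0.08/3 = 2.7% |
| 0.3 | 30% | 29.9% / 22.5% | -2.97 | -2.92 | 0.08/3 = 2.7% |
| 0.6 | 15% | 15.4% / 6.9% | -2.99 | -2.83 | 0.17/3 = 5.7% |
| 0.6 | 30% | 30.1% / 16.5% | -2.98 | -2.77 | 0.23/3 = 7.7% |
| 0.9 | 15% | 15.0% / 4.3% | -3.03 | -2.71 | 0.29/3 = 9.7% |
| 0.9 | 30% | 30.1% / 11.5% | -3.03 | -2.60 | 0.40/3 = 13.3% |

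Measured against the all-visits estimate from the same runs, the range is 1.0% (1 - 2.92/2.95) to 14.2% (1 - 2.60/3.03).

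**Scale.** With all visits, Sxx = 143 x (30/365.25)² = 0.965, so the variance per participant is 16 + 9/0.965 = 25.3. The SE of the difference is √(25.3 x (1/7 + 1/28)) = 2.13. Simulation error is 2.13/√4000 = 0.03. The attenuation of 0.08 to 0.40 points is 4% to 19% of one SE.

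**No treatment effect (both arms 4).** The placebo slope is understated (3.15 to 3.91). The between-arm difference moves by only 0.01 to 0.03 points from its all-visits value, at most 0.03/2.13 = 1.4% of one SE.

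**4. Per-protocol set.** SAP section 6 requires all 9 infusions, so anyone stopped early leaves it. If the fastest of 7 placebo progressors is left out, the expected placebo mean slope falls by 0.22 SD; if the fastest two are, by 0.42 SD.

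**The case against.** The strongest reply is that item c is an ordinary safety provision and that several features limit the bias. Much of this stands.

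- **Discretion.** A reader might infer that every exclusion criterion is automatically re-applied and the fastest progressors removed. The text does not say so: the list is permissive, and item c requires a risk-benefit judgement.
- **Threshold events.** A reader might equate d and e with Huntington progression itself. They are threshold events, and Protocol 1.3 notes that emotional and behavioural changes are not uniform across patients. They can reflect progression; they do not define it.
- **Motor primary.** Protocol 8.7 and the SAP analyse the motor score, and SAP 7.6 replaces the protocol analysis. For TMS the link is an assumed correlation.
- **Data kept.** UHDRS is done at every visit, so scores up to withdrawal stay in the model. Protocol 7.4 requires the V11 assessments when an extraordinary visit leads to withdrawal, and SAP 7.1 assigns early-termination data to the nearest scheduled visit. This captures the last status but not the later course.
- **Other routes.** Items b and h permit similar withdrawals, so editing item c alone would not close the gap. Hence the fix also covers h. Under the footnote to item b, adverse-event cases are followed to resolution and their data considered for efficacy.
- **A larger figure.** In another assumed setting (true difference -2, 20-32% of placebo withdrawn) the plain observed difference at V11 shrinks by 19-27%. That is not the planned estimator; the mixed-model shrinkage there is 4.2% (1.91 to 1.83) to 10.5% (2.19 to 1.96).
- **Timing.** SAP 4.1.2 reports in the past tense that all participants had MRI at V-3 and V11. Collection may be complete and withdrawals few.

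One reply fails: the schedule's exemption of items d and e concerns the inclusion criteria of those letters (motor score and functional capacity), not exclusion items d and e.

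**Conclusion.** The point holds in a limited form. The plan's own rules let a discretionary decision to stop infusions also end outcome collection, for reasons that can be related to severity, with no firm sensitivity analysis to cover it. The overlap is direct for the cognitive and behavioural endpoints and indirect for the TMS slope.

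For the TMS slope the expected harm is modest: about 3-13% attenuation of a real effect in the mixed model. That range rests on the assumed slope, SDs, correlations of 0.3 to 0.9 and placebo withdrawal of 15-30%, none of which comes from the documents; fewer withdrawals would do less.

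A reader might infer a risk of a false positive. The documents do not support that if the discretion is used equally under the blinding in Protocol 6.5. The case for acting is that each placebo exit costs 14.3% of the arm and the remedy is cheap. Whether d or e should stop infusions is clinical and is not judged here.

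**What to change.** 1. **Protocol 5.2.3 (heading and item c), 5.5 and 7.5.** Reconcile these so that stopping infusions is separate from leaving the study. Keep the scheduled UHDRS to V11 for consenting participants whose infusions are stopped, including under items c and h. The sponsor should also state whether exclusion items d and e apply after randomisation when the cause is Huntington's disease.
2. **SAP 7.2.1.** Replace the optional MNAR work with one planned delta-adjusted multiple-imputation (tipping-point) analysis of the TMS slope, for participants whose data stop under 5.2.3(c) or (h), with the range of deltas fixed in advance.
3. **Reporting.** In the disposition table (SAP 7.3.1), give the reasons by arm so that exits linked to Huntington progression can be seen.

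Cost: a few visits already in the schedule and one more analysis, which will rest on few cases. If data collection is already complete, only the SAP change and the reporting of reasons by arm remain possible.

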5.3. Selection failure

The occurrence of participants who sign the informed consent and are not eligible before randomization will be considered a selection failure. All clinical records for participants representing selection failures will be collected in the source document. All participants considered selection failures will be replaced.

The rescreening of participants who failed to meet the inclusion and/or exclusion criteria will be allowed, if the criteria are reversible and may re-fit the eligibility criteria.

5.4. Replacement of study participants

Only participants considered selection failures will be replaced. There will be no replacement for those who are discontinued after randomization.

^a In cases where there is loss of follow-up of the research participant, defined as "no return of the participant on the scheduled date", the Research Center should make telephone contact within a maximum period of one (1) business day after the scheduled visit. The procedure must be registered in a source document, and the new scheduled visit, respecting the maximum period of two (2) days. In situations where the telephone contact is not effective, a telegram should be sent to the research participant requesting the contact urgently. After two (2) telegrams with an interval of 5 working days, the participant of the research should be classified as abandonment. Telephone contact attempts as well as confirmations of receipt of telegrams must be recorded/attached to the source document of the research participant.

^b Participants whose permanence in this study is interrupted by adverse events should be followed up until the resolution of the event. Their data will be included in the adverse event notification forms and considered for the efficacy and safety assessment of the investigational product used in this study.

5.5. Follow-up of research participants whose continuation in this study is interrupted

Research participants excluded due to the emergence of adverse events (AEs) of any extension, related to the use of the product or not, will be monitored by the Research Center and monitored by Sponsor until its outcome. All necessary support will be provided for their clinical condition to be restored, i.e. stabilized at an acceptable level in the Investigator's assessment, and the costs are paid by Sponsor.

Research participants excluded for other particular reasons or for noncompliance with one of the study criteria will not be followed up once the nonoccurrence of AEs has been established.

5.6. Recruitment strategies

Participants will be recruited for a natural demand from people diagnosed with Huntington's disease after the study is released under the regulatory rule of disclosure of clinical studies.

This recruitment strategy is considered specific for the target population and therefore presents a high eligibility rate for participants with diseases considered rare.

6. STUDY TREATMENT

6.1. Identification of the investigational product

The Cellavita-HD product contains viable human mesenchymal stem cells of allogeneic deciduous tooth pulp (of the same species but genetically different), in the form of a liquid suspension, as described in Table 01. The cells are not genetically modified.

Table 01. Description of Cellavita-HD investigational product

Product	Cellavita ⁻ HD	
Characteristics and physical status	Liquid suspension of allogeneic cells	
Concentration	1x10 ⁶ Cells	
Excipients	0.9% sodium chloride containing 10% HSA	
Storage conditions	Cryopreservation -196° C	
Pharmaceutical form	Suspension for infusion	
Administration route	Intravenous use	

Data provided by Sponsor

6.2. Treatment groups

The treatment groups will be arranged as follows:

- **G1: Lower dose:** 1x10 dose⁶ cells/by weight range per administration.
- **G2: Higher dose:** 2x10 dose⁶ cells/by weight range per administration.
- **G3: Placebo:** constituted by the vehicle of the investigational product.

6.3. Dosage

In this study, two different doses of the investigational product will be evaluated ($1x10^6$ cells/by weight range and $2x10^6$ cells/weight range) compared to placebo. Therefore, each participant will receive according to randomization, one of the fractional doses of Cellavita-HD product in 0.9% saline or placebo.

Each participant will receive three cycles of three consecutive administrations (one every 30 days) with the drug according to randomization. The interval between cycles will be 30 days. The following table also summarizes the distribution of participants among the treatment groups, as well as the dosage and the route to be used.

Table 02. Possible treatment groups in the ADORE-DH study

Group	Dose	Dosage	Administration	Investigative Product	Way
G1	Lower dose	1x10 ⁶ cells/weight range	3 administrations (one every 30 days) per cycle	· Cellavita-HD	Intravenous
G2	Higher dose	2x10 ⁶ cells/weight range	3 administrations (one every 30 days) per cycle		
G3	Placebo	Investigational product vehicle	3 administrations (one every 30 days) per cycle	Placebo	Intravenous

